4.1 Screening/Baseline Visit procedures

Screening: Individuals who express an interest in participating in the study during the recruitment process, either in person, email, or by phone, will be contacted by a researcher. The prospective subject will be asked if he/she is interested in learning more about the study and to be screened for inclusion to the study. This screening will follow a standardized format approved by the IRB. We expect most of the time it will take place by phone, but it could also be done in person. The prospective subject will be asked if he/she is willing to provide basic demographic information (gender, age). The researcher will read the list of exclusion criteria and ask if there is anything on this list that could apply to him or her. The subject does not need to disclose the reason, only that there is at least one item that would be applicable. With the subject's verbal permission, the researcher will continue and ask about medications to screen for medications that could lower the seizure threshold. Subjects will then provide ratings of pain and function using the Pain and Functional Subscales of the Western Ontario and McMaster Universities Arthritis Index (WOMAC). This screening process will reduce the chance of participants coming to the lab for further screening if he or she would be excluded based on demographics, health history, medications, and level of physical function. Following the phone or in person screening, eligible participants will be invited to the Neuromuscular Research Laboratory and scheduled for an appointment.

Laboratory Session 1

The goals of the study and procedures will be explained to the subjects. The consent form will be reviewed and the PI or research assistant will address any questions by the subject. After the consent form is completed and signed, the subject will complete additional forms and questionnaires.

Subjects will complete the following forms:

1. Knee injury history and screening form
2. Screening form for inclusion/exclusion criteria including transcranial magnetic stimulation (TMS), repetitive TMS (rTMS), and electric stimulation contraindications
3. Pain numeric rating scale for current pain and pain over the past week
4. Pain Catastrophizing Scale
5. UCLA Activity Score
6. Western Ontario and McMaster Universities Arthritis Index (WOMAC)

The subject will then undergo baseline testing – see study evaluations and measurements in Section 5.

4.2 Intervention/Treatment procedures (by visits)

Laboratory Sessions 2 and 3

Sessions 2 and 3 will be scheduled 1 week apart to allow for wash out of any effects from repetitive TMS (rTMS). The only difference between Session 2 and Session 3 is whether the subject receives rTMS + Exercise or sham rTMS + Exercise. After completing the session 2 pre-testing protocol, the subject will be randomly assigned to receive either the true rTMS or sham rTMS + Exercise intervention. The randomization schedule for the 20 subjects will be generated prior to the onset of the study with assignments only known by the biostatistician. Treatment allocation will be revealed to an investigator performing the rTMS + Exercise intervention after collection of the session baseline measurements. If the subject is allocated to the sham rTMS intervention for Session 2, the subject will receive the "true" rTMS intervention in Session 3 and vice versa.

Measurements from the symptomatic leg only will be made pre and post intervention (true or sham) using the previously evaluations and measurements described in Section 5. Specifically, the pre and post measurements include:

- Pain numeric rating scale (NPRS) for current pain.
- Timed-up-and-go (TUG) - repeated 3 times each time measured
- Pressure pain threshold (PPT) at the 4 leg sites and arm site - repeated 3 times at each site location each time measured
- Thigh muscle function: quadriceps isometric strength (MVIC) and central activation ratio (CAR),
- Single-pulse and double-pulse TMS for cortical and subcortical excitability -
- active motor threshold motor evoked potential (AMT-MEP), cortical inhibition (SICI), and cortical facilitation (ICF)

Repetitive TMS (rTMS) + Exercise Protocol

The protocol for the rTMS is based on a careful review of the literature to optimize the stimulus parameters. As previously described, we will use the single-pulse TMS to find the "hot spot" or optimal location for eliciting the thigh muscle response and to establish the active motor threshold (AMT). Keeping the TMS coil in position, we will follow guidelines established for rTMS (Rossini, 2015). To deliver pulses in a series over time (repetitive TMS), we will use the Magstim Rapid2 device. The device will be set to deliver a total of 750 pulses over a period of 15 minutes. The frequency of the repetitive pulses is set to 10 Hz. The intensity is set at 70% of active motor threshold (AMT). The pulses will be delivered for 5 seconds (on) and 55 second off. During the on time, the subject will perform an isometric exercise for the thigh muscle at 5% of their maximum (MVIC). The subject will rest during the off interval to minimize fatigue. The ratio of "on" to "off" stimulus of rTMS well exceeds the recommended safety guidelines for rTMS maximum safe duration (Wassermann, 1998). These guidelines recommend that the "off" time be at least twice as long as the duration of the "on" time. We are using a 1:11 ratio.

For sham rTMS + Exercise we will maintain the position of the TMS coil for localizing the optimal thigh muscle response. Mu-metal will be placed between the coil and the scalp. The mu-metal serves as a shield for preventing most of the magnetic energy transmission. The coil will be encased in a black mesh bag to allow cooling but hide the mu material. During the "true" rTMS condition, we will also use the mesh bag over the coil to blind the condition. This procedure is similar to one being used by [name], PT, PhD, an investigator at the Medical University of South Carolina (MUSC). [name] designed this in consultation with [name], who has conducted a number of studies using sham rTMS. The immediate effects of rTMS + exercise on the symptomatic knee will be assessed by repeating the outcome measures for the post-test. For session 3, subjects

will return to the lab 1 week after session 2. This will provide sufficient time to “wash out” the effects of the rTMS.

A considerable body of research exists for the use of rTMS for cortical stimulation for rehabilitation of stroke (Le, 2014; Chieffo, 2014; Pollack, 2014), spinal cord injury (Tazoe, 2015; Boldt, 2014) and chronic pain (Galhardoni, 2015; Klein, 2015). [name] has received training rTMS from the National Center of Neuromodulation for Rehabilitation, an NIH sponsored center at the Medical University of South Carolina. The Magstim Rapid2 has FDA clearance (510k) for treatment of drug resistant Major Depressive Disorder and for peripheral stimulation. Magstim devices are considered to be investigational for rehabilitation use in the USA for cortical stimulation, yet we have requested an IDE for this device as it has been safely and successfully used on clinical and healthy populations. We are conducting this study to determine if rTMS + exercise can acutely alter corticospinal excitability of the quadriceps in people with knee OA. Improving corticospinal excitability in patients with quadriceps dysfunction secondary to knee OA may allow for improved muscle function, thereby improving self-reported function and physical activity. This is a first step in testing a neurophysiological principle. According to the Magstim company, in 4 out of 5 carried out on TMS, the researchers have used Magstim products. A number of areas of study and references are available for review.

4.3 Follow- up procedures (by visits)

N/A

4.4 Unscheduled visits

N/A

4.5 Concomitant Medication documentation

N/A

4.6 Rescue medication administration (if applicable)

N/A

4.7 Subject Completion/ Withdrawal procedures

Participants may withdraw at any time in the study. Participants will be monitored throughout the study for any adverse events and will be withdrawn from the study if they report any adverse events associated with either the testing or the intervention. In the event that a participant sustains an injury during the study, they will be referred to the appropriate medical personnel on campus (i.e. Campus Health Services or the UNC Hospitals Emergency Room). Most women enrolled will not be of childbearing age. If patients are pregnant or plan to be become pregnant during the study we will exclude these patients from the study as these changes may have an effect on the physiology that could alter the response to the rTMS and other measures.

Individuals will be withdrawn from the study if they experience any of the following:

- 1) Signs of musculoskeletal injury
- 2) Failure or inability to comply with the study procedures
- 3) Any sign of moderate or severe adverse effects associated with TMS or rTMS.
- 4) Pregnancy

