Follow-Up	(4) Intervention (double-blind, crossover) : Arm 1: Session 1 = rTMS and exercise; Session 2 = sham rTMS and exercise Arm 2: Session 1 = sham rTMS and exercise; Session 2 = rTMS and exercise
Efficacy Evaluations	Quadriceps maximal voluntary isometric contraction (MVIC) Change in Quadriceps Central Activation Ratio (%)
Pharmacokinetic Evaluations	NA
Safety Evaluations	Adverse events will be determined using the NC TraCS Safety Monitoring Plan guidelines for Minimal Risk Studies. The Grading Scale is as follows: Mild - Event results in mild or transient discomfort, not requiring intervention or treatment; does not interfere with daily activities (e.g. transient muscle soreness) Moderate - Event is sufficiently discomforting so as to limit or interfere with daily activities; may require additional interventional treatment (e.g. musculoskeletal injury such as a muscle strain) Severe - Event results in significant symptoms that prevent normal daily activities; may require invasive intervention In the event that two adverse events are classified as either moderate or severe the study will be placed on hold in order to reassess the study procedures in order to decrease the risk of another adverse event.

Statistical And Analytic Plan	
Aim 1: We will compare between limb differences and use correlation analyses to examine associations between measures of neural excitability, pain, pain sensitization, quadriceps function, timed-up-and-go test, and pain catastrophizing.
 
Aim 2: We will use a repeated measures analysis of variance (ANOVA) to compare the pre- and post-intervention outcomes.

DATA AND SAFETY MONITORING PLAN	
In the event that two adverse events are classified as either "moderate" or "severe", based on the NC TraCS Safety Monitoring Plan guidelines, the PI will place the study on hold in order to reassess the study procedures to decrease the risk of another adverse event.
 
Individuals will be withdrawn from the study if they experience any of the following:
 
1) Signs of musculoskeletal injury2) Failure or inability to comply with the study procedures3) Any sign of moderate or severe adverse effects associated with TMS or rTMS.4) Pregnancy

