Infrequent: Muscle soreness and knee joint soreness from contracting the quadriceps may occur, but will be minimal and the soreness should go away within a day. The thigh muscle contractions during the muscle strength testing may infrequently result in muscle soreness or, in extremely rare cases, muscle injury. Participants will be provided with warm-up exercise before completing these tasks and provided adequate rest breaks between tasks in order to reduce the risk of injury.

Some people report mild discomfort when the TMS pulses are applied over the scalp. A small number of people (~5%) report headache following rTMS. However, the headaches are temporary and manageable with common over-the-counter pain remedies.

Rare: There is a possibility of discomfort associated with prepping the areas where electromyographic (EMG) sensors will be placed (i.e. shaved, lightly abraded, and cleaned with alcohol).

Syncpe is defined as a momentary loss of awareness and postural tone. It typically has a rapid onset, short duration, and spontaneous recovery. Although syncopal episodes are very rare with TMS (less than 1%), they typically occur during the motor threshold procedure before the rTMS treatment has begun. Individuals that are sleep deprived and have low or unstable blood pressure are at greater risk. The participant's blood pressure and pulse will be taken prior to data collection. Fainting due to a sudden drop in blood pressure is called syncpe. Syncpe with TMS and rTMS is rare and occurs at a rate similar to other medical procedures such as drawing blood. However, anyone with low blood pressure (< 90 systolic and < 60 diastolic) or slow heart rate (< 50 beats per minute) or feeling light headed will be excluded from continuing on to the TMS testing.

Regarding sleep deprivation, in our intake Knee History Questionnaire, the participant is asked about their sleep in the past 24 hours to determine if he/she may be sleep deprived. The questions specifically are: How many hours of sleep did you get last night? _____ Is this normal for you? No Yes

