3.4 Study Population

Subjects will be between 40 and 75 years old. Participants must exhibit symptomatic knee osteoarthritis involving one leg, which we will define as a normalized, person based, Western Ontario and McMaster Universities Arthritis Index (WOMAC) function subscale score of 10 or more points or 14.7% (out of 100 %, indicating most dysfunction). When radiographs of the knee are examined for osteoarthritis, the arthritis will be judged to be between a 2 to 4, based on the Kellgren – Lawrence scale. The opposite knee should be relatively asymptomatic with WOMAC pain score ≤ 5 . If radiographs are available, the opposite knee should score ≤ 2 on the Kellgren-Lawrence scale.

Potential participants will be excluded if they have orthopedic conditions affecting the leg other than knee osteoarthritis, conditions that could limit their exercise tolerance, pregnancy, conditions that could alter sensation and pain processing, and conditions that are of concern for using repetitive transmagnetic stimulation (rTMS). We have incorporated published safety guidelines for repetitive transcranial magnetic stimulation (TMS) to screen subjects (Wasserman, 1996; Rossi, 2009; Rossi, 2011; Rossini, 2015;):

The full list of exclusion criteria, including those for transcranial magnetic stimulation, for this research includes:

- A body mass index (BMI) > 35
- Low blood pressure (< 90 systolic, 60 diastolic) or heart rate (< 60 beats per minute)
- Pregnant or planning to become pregnant in the next 3 months
- Require a cane, walker, or crutches to walk
- Heart condition or disease that restricts exercise
- History of low back surgery in the past year
- History of leg orthopedic surgery in the past year
- Injection (corticosteroid or hyaluronic acid) in either knee in the past 4 weeks
- Knee replacement surgery
- Knee ligament tear that did not undergo reconstruction (ACL, MCL)
- Severe arthritis in both knees
- Knee ligament tear that did not undergo reconstruction (ACL, MCL)
- Cancer in the thigh area (bone or muscle)
- Fibromyalgia
- Uncontrolled diabetes with numbness and tingling in legs or arms
- Peripheral neuropathy (numbness, tingling in extremities)
- A balance disorder
- Had an adverse reaction to an MRI or Transcranial Magnetic Stimulation (TMS)?
- Seizures or epilepsy
- Have had a stroke
- Have had a head injury (including neurosurgery)

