The participant rates their level of physical activity. The range is from 1, defined as “no physical activity, dependent on others” to 10, defined as ““regular participation in impact sports.” It has been shown to have construct validity for monitoring physical activity with knee OA (Terwee, Bouwmeester, et al 2011).

Western Ontario and McMaster Universities Arthritis Index (WOMAC)

The Western Ontario and McMaster Universities Osteoarthritis Index (WOMAC) (Bellamy, Buchanan et al. 1988) (Hawker, Wright et al. 2001) (Mahomed, Liang et al. 2002) (Hawker, Wright et al. 1998) (Bullens, van Loon et al. 2001) is one of the most commonly used patient-reported outcome measures for knee OA, provides ratings of pain severity during various positions or movements, severity of joint stiffness, and difficulty performing daily functional activities (Collins, Misra et al. 2011). Each item is scored from 0 to 4 with higher scores indicating worse pain, stiffness, or physical function. The total score for each subscale is determined by adding the items. A total score from 0 (no problems) to 96 (extreme problems) can be calculated. The WOMAC has moderate to good reliability for the three subscales (ICC $> .75$) (Gandek 2015) and an MCID of 4-9 points (Williams, Piva et al. 2012).

Vital Signs

The participant's blood pressure and pulse will be taken prior to data collection. Fainting due to a sudden drop in blood pressure is called syncope. Syncope with TMS and rTMS is rare and occurs at a rate similar to other medical procedures such as drawing blood. However, anyone with low blood pressure (< 90 systolic and < 60 diastolic) or slow heart rate (< 50 beats per minute) or feeling light headed will be excluded. In our intake Knee History Questionnaire, the participant is asked about their sleep in the past 24 hours to determine if he/she may be sleep deprived.

How many hours of sleep did you get last night? _____ Is this normal for you? ? No ? Yes

If the subject reports less than 7 hours of sleep we further explore the sleep pattern. We will ask the participant if this is a normal amount of sleep for him/her and if he/she had a nap in the past 24 hours. If the total reported amount of sleep is off by 2 hours or more compared to their normal pattern, we will consider this a sign of sleep deprivation and the subject will be rescheduled for another time.

Timed-Up-And-Go Test (TUG)

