9 SAFETY MANAGEMENT

The principal investigator, [name], will oversee data collection monitoring and all issues related to participant safety, data collection protocols, and participant confidentiality. [name] will personally collect any adverse event that occurs during the data collection sessions in the Sports Medicine Research Laboratory.

The participant's vital signs will be taken before any active testing, TMS, or rTMS. If the blood pressure or heart rate is low (< 90 systolic, < 60 diastolic, < 50 beats/min), the participant will be advised of the higher risk of syncope and excluded. If the participant reports being light headed or sleep deprived, the data collection session will be stopped and rescheduled.

All researchers involved with TMS and rTMS will be trained on management of syncope and seizures. We will minimize risk of seizure by screening participants for a seizure history and tailoring each person's TMS intensity to their motor (and indirectly seizure) threshold. We will exclude subjects if they are taking medications that are linked to reducing seizure thresholds. We will minimize hearing damage from rTMS by having all participants wear earplugs to protect their hearing during the TMS sessions.

Before maximum voluntary isometric contraction (MVIC) testing participants will be given a warm-up. Participants will also go through a graded warm up to acclimate to the stimulation needed for quadriceps voluntary activation testing. The 5-minute warm-up prior to testing is designed to reduce the risk of muscle soreness and/or injury during testing. The electrical stimulator will always be connected to the stimulus isolation unit to ensure that the subject is isolated from fluctuations in the building's power supply. Additionally, most members of the research team are certified/licensed health

care providers (Licensed Physical Therapist or Certified Athletic Trainer), and all are trained and certified to provide First Aid and CPR. Any safety concerns (i.e. musculoskeletal injury) would likely be recognized immediately during testing and the research team will monitor participants for adverse events during both testing and intervention sessions.

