The research team will refer any individuals who experience adverse events to the Stallings-Evans Sports Medicine Center (located in the building adjacent to Fetzer Hall where the Neuromuscular and Sports Medicine Research Laboratories are located) or Emergency Medical Services depending on the nature and severity of the adverse event issues.

Adverse events will be determined using the NC TraCS Safety Monitoring Plan guidelines for Minimal Risk Studies. The Grading Scale is as follows:

Mild - Event results in mild or transient discomfort, not requiring intervention or treatment; does not interfere with daily activities (e.g. transient muscle soreness)

Moderate - Event is sufficiently discomforting so as to limit or interfere with daily activities; may require additional interventional treatment (e.g. musculoskeletal injury such as a muscle strain)

Severe - Event results in significant symptoms that prevent normal daily activities; may require invasive intervention

In the event that two adverse events are classified as either moderate or severe the study will be placed on hold in order to reassess the study procedures in order to decrease the risk of another adverse event.

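### The rules for withdrawal, low heart rate and light-headedness differ between sections and must be reconciled

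*Combined protocol and SAP*

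**What the plan says.** **Withdrawal.** Section 4.7 states that participants "will be withdrawn from the study if they report any adverse events associated with either the testing or the intervention". Sections 1.2, 5.3 and 6.2 carry the same sentence, with no severity limit. A four-item list of withdrawal grounds stands in the synopsis, 4.7 and 6.2: signs of musculoskeletal injury, non-compliance, pregnancy, and "Any sign of moderate or severe adverse effects associated with TMS or rTMS".

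**Severity scales.** In Section 9 and the synopsis, a mild event needs no intervention or treatment and "does not interfere with daily activities (e.g. transient muscle soreness". A moderate event limits daily activities and "may require additional interventional treatment (e.g. musculoskeletal injury such as a muscle strain". Section 5.3 prints a different scale, on which a mild event may still be treated with non-prescription measures.

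**Heart rate.** The exclusion list in 3.4 names low blood pressure "or heart rate (< 60 beats per minute". Sections 1.2 and 5.3 say that anyone with low blood pressure "or slow heart rate (< 50 beats per minute) or feeling light headed will be excluded from continuing on to the TMS testing". Section 5 (Vital Signs) has a shorter version: "or slow heart rate (< 50 beats per minute) or feeling light headed will be excluded". Section 9 begins "If the blood pressure or heart rate is low (< 90 systolic, < 60 diastolic, < 50 beats/min", and such a participant is warned about syncope and excluded.

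**Light-headedness.** The sentences quoted from 1.2, 5 and 5.3 put it together with low blood pressure and slow heart rate. Section 9 puts it together with sleep deprivation: the session is halted and booked for another day.

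**The concern.** These are operating rules for a study that itself names syncope and seizure as risks. Two staff members working from different sections could treat the same participant differently in three situations: a mild event linked to testing or intervention, a resting heart rate of 50 to 59, and light-headedness at a session.

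The main stakes are participant safety and uniform conduct. There is also a statistical stake. Aim 2 is a crossover in 20 people, and each participant contributes a full comparison only if both intervention sessions are completed. A rule that removes people for mild events therefore affects how many supply both periods. Some of those events, such as headache after rTMS, are expected mainly after the active session.

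**Working it through.** The plan gives no expected number of withdrawals, so there is no figure to reproduce. The check is a comparison of the text, followed by an illustration of size.

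**1. Withdrawal rule by section**

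| Section | Any-event sentence | List with the moderate/severe qualifier |
|---|---|---|
| Synopsis | no | yes |
| 1.2 | yes | no |
| 4.7 | yes | yes |
| 5.3 | yes | no |
| 6.2 | yes | yes |

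The clearest evidence lies inside 4.7 and 6.2. If every associated event leads to withdrawal, restricting stimulation effects to moderate or severe ones adds nothing. If the restriction is meant, the sentence is too broad.

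Transient muscle soreness is a test case. Section 9 gives it as its example of a mild event and gives musculoskeletal injury as an example of a moderate one, so soreness is not the first list item. It triggers withdrawal under the sentence and is not triggered by any list item.

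**2. Severity scale.** Sections 1.2 and 5.3 describe headache after rTMS as manageable with over-the-counter remedies. A headache treated that way can be mild on the 5.3 scale. It is not clearly mild on the Section 9 scale, which allows no treatment at that grade. The third list item therefore depends on which scale applies, and the list names none.

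**3. Heart rate.** Section 3.4 uses below 60; Sections 1.2, 5, 5.3 and 9 use below 50. The only pulse measurement described is the one taken before data collection or active testing. At Session 1 that one reading faces both limits. At Sessions 2 and 3 no passage says which limit governs a reading of 50 to 59.

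**4. Light-headedness.** Section 5 says excluded, while its next sentences reschedule the sleep-deprived. Section 9 excludes for low vital signs but reschedules the light-headed. Each section uses the two words for different outcomes and places light-headedness on a different side. The wording in 1.2 and 5.3 fits either.

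**5. Size, illustrative.** Inputs from 1.2 and 5.3: soreness more than 1% and up to 10%; headache about 5%; discomfort from the electrical stimulus above 50%; N = 20. Assumptions: these are per-participant probabilities, and soreness and headache are independent.

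- Soreness and headache only, meeting the any-event rule: 20 × (1 − 0.99 × 0.95) = 1.19, up to 20 × (1 − 0.90 × 0.95) = 2.90.
- Fewer would lose outcome data, because effects are evaluated within a session and 4.3 has no follow-up. Take 10 per sequence, two thirds of soreness before Session 3, and headache after the active session. Low: 10 × (1 − 0.99333 × 0.95) + 10 × 0.00667 = 0.563 + 0.067 = 0.63. High: 10 × (1 − 0.93333 × 0.95) + 10 × 0.0667 = 1.133 + 0.667 = 1.80.
- Stimulation discomfort counted as a mild event, at exactly 50%: 20 × 0.5 = 10, and more above that rate. The chance that fewer than 11 of 20 remain is P(Binomial(20, 0.5) ≥ 10) = 0.59.

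The 11 is the number needed in 6.4. It is not a firm benchmark: with effect size 0.84, a one-sided paired t-test gives 11 (power 0.83), but a two-sided one gives 14, with power 0.71 at 11.

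**The case against.** A fair defence has four parts.

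First, the list nowhere says that it is exhaustive, so list and sentence can be applied together, and the synopsis may simply be abridged. This stands in part. A reader might infer that the synopsis permits withdrawal only on its listed grounds, and so flatly contradicts 1.2 and 5.3; the text does not support that. The list is the same in all three places, and the synopsis is no more restrictive than 4.7 or 6.2. What the defence cannot explain is why the list carries a severity qualifier.

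Second, 60 could be an entry limit and 50 a session-day limit. Section 3.4 calls its list full, and eligibility criteria are cumulative. A reader might infer that the four sections using 50 clear a person at 50 to 59. None of them says so. What remains is an unexplained difference, with no two-tier rule stated.

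Third, the Section 5 sentence on light-headedness may be a shortened copy of the one in 1.2 and 5.3, where the exclusion is from going on to TMS testing. That is plausible. Permanent removal of a light-headed participant should not be read into it, which makes this a lesser point.

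Fourth, the statistical effect might be called negligible because only 1 to 3 people would meet the rule. That does not follow. It counts two kinds of event, whereas Section 9 defines a mild event as mild or transient discomfort and 5.3 puts stimulation discomfort above 50%.

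**Conclusion.** The inconsistencies are in current text and should be fixed. The firmest are the any-event sentence against the graded list, visible inside 4.7 and 6.2, and the unexplained limits of 60 and 50 beats/min. The difference between the two severity scales adds to the first. Light-headedness is a secondary wording conflict between Sections 5 and 9.

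No single figure for size should be relied on. The range runs from about 1 to 3 of 20 meeting the any-event rule, if only soreness and headache count, to half or more if stimulation discomfort counts. Both ends treat the protocol's incidence classes as per-participant probabilities, and the lower end also assumes independence. The documents do not show that the sponsor intends the upper end; it is what the sentence and the Section 9 scale give when read literally. The case for the change rests mainly on safety and consistent conduct.

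**What to change.** Reconcile the passages and print each rule in the same words wherever it appears:

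- One withdrawal rule in the synopsis, 1.2, 4.7, 5.3 and 6.2, tied to one named severity scale. Either align the scales in 5.3 and Section 9 or say what each is for. State whether expected discomfort from the test procedures counts as an adverse event for this rule.
- One heart-rate limit in 1.2, 3.4, 5, 5.3 and 9, or an explicit statement that the entry and session limits differ and which applies at each visit.
- One stated consequence of light-headedness in 1.2, 5, 5.3 and 9.

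Which trigger, limit and consequence to adopt is for the sponsor and safety reviewers to decide. The cost is amendment wording, with no added procedures, staff or participants.
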